1.0 INTRODUCTION

Breast cancer is the most common cancer experienced by women, and an estimated 4 million American women are breast cancer survivors.¹ Many of these women must take ongoing medications after adjuvant treatment to further reduce the risk that the cancer returns. Aromatase inhibitors (AIs) are commonly indicated for this purpose. AIs reduce hormone receptor-positive (HR+) breast cancer recurrence by decreasing the level of serum estrogens in postmenopausal women.² However, AIs can cause significant side effects that reduce patient adherence. Although estimates vary based on the population surveyed, between 20-55% of women report occasional to frequent non-adherence.³⁻⁵ Early discontinuation of AI therapy results in an increased risk of cancer recurrence and increased risk of breast cancer-related death.⁵ Common side effects include vaginal dryness and vulvovaginal atrophy leading to worsening sexual function.⁶ This is because normal vaginal lubrication depends on the bioavailability of nitric oxide (NO) in the vaginal epithelium, and this is greatly enhanced by steroid hormones (i.e. estrogen).^{7,8} Additionally, the estrogen deprived state of menopause leads to decreased acidification of the vagina (increased pH) which is strongly correlated with

vaginal health.⁹ Unfortunately, the increased circulating estrogens from systemic and vaginal hormone replacement therapies may be detrimental for women with HR+ breast cancer due to proven or suspected increase in breast cancer risk.^{10,11} Non-hormonal treatments to decrease vulvo-vaginal side effects and improve adherence to life-saving therapies are lacking and severely needed.

An alternative mechanism for stimulating NO production occurs when vaginal capillary endothelia are exposed to sheer stress or vibration.¹² This mechanism is proposed to explain the symptomatic benefits accrued by the Vaginal Renewal Program (VRP) participants. The physical therapy program known as the VRP was created in 1998 by [name], MSW and [name].⁹ The VRP employs a therapeutic vibrating wand used in the vagina. This was developed specifically to address concerns common among cancer survivors experiencing vulvovaginal atrophy and dryness. The vibrating wand is approved as class I durable medical device by the US Food and Drug Administration (FDA). The VRP was created to improve symptoms of vulvovaginal atrophy and vaginal dryness - two of the most commonly experienced side effects that lead to AI discontinuation. The VRP is outlined below under *Intervention*. Despite being developed in 1998 and in routine clinical use, little published data exists to support changes in vaginal physiology or symptomatic benefit from the VRP. As a result, the VRP is not covered by insurance and cannot be made widely available to women.

2.0 STUDY HYPOTHESIS & OBJECTIVES

2.1 Hypothesis

We hypothesize that the percentage of superficial vaginal cells on cytology evaluation as well as vaginal pH will improve after 3 months of using the VRP in menopausal subjects receiving maintenance AIs for Stage 0-3 hormone receptor-positive breast cancer.

2.2 Primary Objective

To assess for an increase in the percentage of superficial vaginal cells on a cytology evaluation after 12 weeks of VRP use. The reason vaginal cytology is being measured is because it is the method of choice for objective evaluation of vaginal atrophy.¹³ Vaginal cytology has been used to prove the efficacy of other therapies that improve symptoms of vaginal dryness and atrophy.¹⁴ The 3-month time point is being used because multiple prospective studies using hormonal therapies to improve vulvovaginal atrophy used this as the primary time point to assess efficacy.¹⁵⁻²⁰ Assessment parameters for superficial vaginal cells is taken from this literature.^{15,16,20}

2.3 Secondary Objectives

2.3.1 To evaluate changes in vaginal pH from the baseline time point to 12 weeks after initiating the VRP in the same patient population.

2.3.2 To evaluate changes in patient-reported outcomes (PROs) (**see SECTION 9.1.3**) in the same population between the baseline time point to 12 weeks after initiating the VRP.

2.4 Exploratory Objectives

2.4.1 To assess percentage of subjects who adhere at least 90% to AI therapy throughout the course of the study.

3.0 STUDY DESIGN OVERVIEW & RATIONALE

We will utilize a prospective Simon two-stage Phase II study design. Breast cancer patients who have completed primary active therapy for breast cancer (e.g. surgery, chemotherapy and/or radiation) and are currently taking maintenance aromatase inhibitors (AIs) such as anastrozole, letrozole or exemestane will be approached. We will assess response to the VRP with a blinded standardized interpretation of superficial vaginal epithelial cells. Entrance criteria will stipulate baseline measurements must be < 2%. If the subject has $\geq 4\%$ superficial vaginal cells on cytologic evaluation after the intervention period, then the response will be considered positive.

After documentation of eligibility according to the inclusion and exclusion criteria (**see Section 5.0**) and after enrollment, the subject will receive instruction in the VRP (**see Section 6.0** for details and **Study Schema**). Baseline demographic data, baseline vaginal cell cytology, vaginal pH, and PROs will be collected prior to initiating the VRP instruction. During the time on study, subjects will log their adherence to the prescribed therapy schedule of the VRP and AI therapy. Subjects will receive reminder contacts from study staff/team member 1 week and 1 month after initial instruction. These calls will function to ensure that subjects have had adequate instruction, and problem-shoot any issues with adherence to the program and logging adherence. The subject will return the journal at the 12-week study completion visit when vaginal cell cytology, vaginal pH, and PROs will be assessed.

The primary endpoint of percent superficial vaginal cells will be determined via blinded review by a board-certified pathologist experienced with interpretation of cytology. Secondary endpoints of pH will be logged at the time of the exams and PROs will be determined by standardized, validated scoring metrics for the respective PRO measures used. The exploratory analysis of AI adherence will be determined using patient-reported logs.

4.0 RECRUITMENT AND ENROLLMENT

4.1 Design

A non-randomized, single-arm Simon phase II design will be used with participants who are eligible and give informed, written consent.

4.2 Recruitment

Subjects will be recruited with the assistance of the UWCCC research staff..

To increase accrual, the research staff will employ the following strategies:

- 1) Study staff will identify current patients with Stage 0-3 breast cancer who are receiving aromatase inhibitors (anastrozole, letrozole or exemestane). Study staff will focus on patients who have upcoming follow-up visits at the UW.
- 2) Identified patients may be sent a letter or a MyChart message briefly describing the study (see script in Appendix 2)
- 3) Patients who receive the letter or message will be asked in the letter or message to contact the research staff via phone or email within a 7-day time-frame if they **do not wish** to be approached with information about the study (“opt-out”).
- 4) Research staff will contact patients who do not opt-out. Research staff will attempt to contact patients, via phone, up to 3 times over the course of 2-3 weeks to discuss

their interest in learning about the study. At the time of the phone call, patients may decline this conversation if they are not interested in the study. See script in Appendix 3.

- 5) For patients that staff are not able to contact or who wish to delay the conversation, the research staff will notify the treating physicians to discuss the study further at the time of the clinic visit.
- 6) For interested patients, research staff will review the trial by phone or in person. With the patient's permission, research staff may ask questions related to medications, recent surgery or anti-cancer therapies and menopausal status to determine gross eligibility.
- 7) To obtain final consent, enroll subjects into the study and complete baseline evaluations, research staff will employ a standard opt-in approach. This would be scheduled at a time convenient to the patient, and would likely coincide with a scheduled clinical follow-up visit. This would reduce the participation burden for interested patients.
- 8) Patients may also be approached by a member of their clinical team when present for a routine clinic visit. The clinic team member will introduce the study to potentially eligible patients. If the patient is interested in learning more about the study, a member of the research team will review the study details and continue with the informed consent process.

4.3 Consented subjects will be registered to the study using the OnCore database by study staff.

4.4 Intervention

All subjects on this study will receive the VRP intervention. Enrolled subjects will receive in-person instruction on how to perform the VRP.

The instructor is a certified sexuality counselor who has been trained in the instruction of the VRP.

The VRP consists of instructing subjects regarding digital physical therapy techniques for the vulva and vaginal introitus as well as internal physical therapy techniques using a therapeutic vibrating vaginal wand designed for the VRP and FDA-approved as a class I durable medical device (FeMani Vibrating Massage Wand). Details of the program are outlined in a brochure that will be provided to participants.

4.5 Study Completion Visit After 12 weeks (+/- 4 weeks) subjects will return to see the provider, return log books documenting adherence to prescribed therapy, have repeat vaginal cell cytology samples and pH testing, and complete post-intervention PRO surveys.

5.0 SUBJECT ELIGIBILITY

5.1. Inclusion Criteria

Each potential subject must satisfy all of the following criteria to be enrolled in the study:

_____ **5.1.1** Females \geq age 18 diagnosed with Stage 0-3 breast cancer

_____ **5.1.2** Have completed active primary treatment

- Defined as surgery, chemotherapy and/or radiation for the treatment of breast cancer
- Does not include immunotherapy or other targeted therapies such as trastuzumab, CDK 4/6 or mTOR inhibitors

_____ **5.1.3** Have been receiving AIs for at least 6 months prior to enrollment

_____ **5.1.4** Plan to continue AIs for an additional 3 months

_____ **5.1.5** Amenorrhea for at least 12 months at enrollment regardless of cause

_____ **5.1.6** Participants must be able to read and write in English

_____ **5.1.7** Participants must have < 2% superficial vaginal cells on cytologic evaluation

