7.2 Program materials

Subjects will receive personal lubricant in sufficient quantity to perform the program per protocol for 12 weeks. They will also receive the FeMani Vibrating Massage Wand free of charge. This a class 1 durable medical device approved by the FDA.

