8.2 Subject replacement

For this study, lack of adherence will be defined as < 3 days/week participation for 2 weeks or

more as assessed on the 1-month phone call. If a subject is found to be not adhering to the study protocol, a new subject will be enrolled in a 1:1 ratio. Subjects lost to follow-up for any reason will be replaced in a 1:1 ratio. All subjects enrolled and not lost to follow-up, regardless of adherence status, will have their data collected and analyzed accordingly.

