9.4 Study Completion Visit

All subjects will be asked to return 12 weeks (+/- 4 weeks) after in-person instruction of the VRP program. Subjects will complete post-intervention PROs prior to undergoing vaginal swab/collection. Subjects will be asked to bring and turn in the logbooks for analysis.

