11.3 Primary Endpoint

We expect the percentage of superficial vaginal cells to be greater at the post-intervention time point when compared to the pre-intervention time point. If the percentage of superficial vaginal cells is $\geq 4\%$ following the intervention, then the response will be considered positive.

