Appendix 1 – Schedule of Events

	Enrollment^a	VRP instruction visit	1 Week Post-Instruction	1 Month Post-Instruction	12-week follow-up visit^d
Informed consent	X				
Eligibility checklist	X				
Baseline demographics		X			
PRO evaluations ^b		X			X
Cytology swab	X				X
pH collection	X				X
VRP Instruction		X			
Collect VRP use logbook					X
Phone Call ^c			X	X	

- A. The enrollment and VRP instruction visit may be conducted at the same time.
- B. The PROs will be: Vaginal Symptoms Questionnaire, NIH PROMIS Global Health scale, NIH PROMIS Female Sexual Function Profile, NIH PROMIS Global Satisfaction with Sex Life scale, NIH PROMIS Anxiety 8a scale, NIH PROMIS Depression 8a scale
- C. Phone calls to assess adherence
- D. +/- 4 weeks

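### The completion swab may be taken up to week 16 after instruction, but entry asks for only 3 more months of planned AI use, so a woman already off AI can count toward the single-arm response rate

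*Combined protocol and SAP*

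**What the plan says.** **AI horizon at entry.** Section 5.1.4 requires "Plan to continue AIs for an additional 3 months". It does not say whether the 3 months run from consent, enrolment or instruction.

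**Timing of the endpoint.** Section 9.4: "All subjects will be asked to return 12 weeks (+/- 4 weeks) after in-person instruction of the VRP program". Section 4.5 and Appendix 1 give the same window, and at that visit subjects "have repeat vaginal cell cytology samples and pH testing, and complete post-intervention PRO surveys".

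**Gap before the clock starts.** Appendix 1: "The enrollment and VRP instruction visit may be conducted at the same time". They may also be separate visits, and no maximum interval is given.

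**What counts as a response.** Sections 10.1 and 11.3 use the cytology result alone, a rise from below 2% to at least 4%: in 11.3, a result at that level "following the intervention, then the response will be considered positive". Neither section mentions AI status at the swab.

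**Handling of AI use.** Section 8.2 defines adherence for the VRP only and judges it once, at the 1-month call. Everyone not lost to follow-up is analysed whatever her adherence. Section 12.2 does not list stopping AI as a reason for withdrawal. Missed AI days are logged weekly (7.3, 9.3), but only an exploratory objective uses the log (2.4.1, 11.6).

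**Supplies.** Section 7.2: "Subjects will receive personal lubricant in sufficient quantity to perform the program per protocol for 12 weeks", and "They will also receive the FeMani Vibrating Massage Wand free of charge".

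**The concern.** The hypothesis in Section 2.1 concerns menopausal women who are receiving maintenance AIs, and 5.1.3 and 5.1.4 appear intended to keep that background stable. The second of these can expire before the endpoint is measured. Section 1.0 says that AIs act by lowering serum estrogens and links estrogen deprivation to the vaginal effects. On that rationale, ending AI before the swab would move superficial cells toward response with no contribution from the VRP.

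The trial has one arm, so no comparison group would show such a drift, and a conversion would be credited to the program. This can happen in a woman who breaks no rule, so deviation reporting would not reveal it. Rejection needs only 6 responders of 25, so a very small number of misattributed responses could matter.

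**Working it through.** **1. Dates.** Latest swab: 12 + 4 = 16 weeks, or 112 days, after instruction (4.5, 9.4, Appendix 1). AI horizon: 3 × 365.25 / 12 = 91.3 days, or 13.0 weeks (5.1.4).

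- Same-day enrolment and instruction: 16 − 13.0 = about 3.0 weeks uncovered.
- Instruction g weeks after enrolment, with the 3 months read as running from enrolment: about 3.0 + g weeks. The documents set no upper limit on g.
- Nominal 12-week visit with same-day instruction: 13.0 > 12, so the swab is covered. The gap opens only for visits after about week 13.

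**2. The plan's own design (Section 11.2).** Inputs: 15 patients in stage 1, stop at 1 or fewer responses; 25 in total, reject at 6 or more; null rate 10%, alternative 30%.

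P(reject) = Σ over x = 2..15 of P[Bin(15, p) = x] × P[Bin(10, p) ≥ 6 − x].

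At p = 0.10 the terms for x = 2, 3, 4, 5 and ≥ 6 are 0.00341 + 0.00902 + 0.01130 + 0.00682 + 0.00225 = 0.0328. At p = 0.30 the sum is 0.802. The stated design reproduces: type I error 3.3%, within the 5% limit, and power of about 80%.

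**3. Illustration with women swabbed off AI.** Let k1 such women fall in stage 1 and k2 in stage 2. Each responds with probability q for reasons unrelated to the VRP, and everyone else responds at 10%. The stage 1 count becomes Bin(15 − k1, 0.10) + Bin(k1, q), and the stage 2 increment becomes Bin(10 − k2, 0.10) + Bin(k2, q). The stopping and rejection rules are unchanged. Both k and q are assumptions, because the documents give neither. The ranges below cover placement in stage 1 or stage 2.

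| Spurious response probability q | One woman | Two women |
|---|---|---|
| 20% | 3.8–3.9% | 4.4–4.5% |
| 30% | 4.4% | 5.7–5.9% |
| 50% | 5.5–5.6% | 8.6–9.0% |
| 100% | 8.2–8.5% | 17.9–19.3% |

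Hand check for one woman in stage 1: the error rate is (1 − q)A + qB, where B = 0.0847 is the rate if she certainly responds. At q = 0.10 it must equal 0.0328, so A = (0.03281 − 0.00847) / 0.9 = 0.0270. At q = 0.20 this gives 0.8 × 0.0270 + 0.2 × 0.0847 = 0.0386. It reaches 5% at q = (0.05 − 0.0270) / (0.0847 − 0.0270) = 0.40.

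**4. Lubricant.** The supply is described as 12 weeks and the visit may be at week 16, a nominal shortfall of up to 4 weeks. Section 6.0 encourages use on 3 to 4 days per week. A supply sized for 4 days covers 4 × 12 = 48 sessions, which at 3 days per week lasts 48 / 3 = 16 weeks. The documents do not say which rate sets the quantity, so a shortfall is possible but not shown.

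**The case against.** The strongest reply is that several things must coincide. Criterion 5.1.4 is a minimum intention, not a stop date. An affected woman must plan to end AI soon after month 3, return late in the window, and convert because of it. At the nominal visit the criterion does its job. This limits the likely frequency and it stands, but nothing in the protocol excludes the case.

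The mechanism is also only directional. Section 1.0 attributes atrophic change to menopause itself as well, participants must have been amenorrheic for 12 months (5.1.5), and current or recent estrogen therapy is excluded (5.2.4, 5.2.5). Nothing in the documents shows that about 3 weeks without AI takes superficial cells from below 2% to 4% or more. That stands too.

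The AI log makes such swabs identifiable. That is true and useful, but no analysis rule uses it for the primary endpoint.

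A reader might infer three stronger things that the documents do not support:

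- That type I error rises to about 8% or 19%. Those figures require one or two women who respond with certainty. At q up to 30%, one woman leaves the error below 5%.
- That the lubricant shortfall also creates false responders. It is not shown to bind, the wand stays with the subject, and a woman who lapsed from the program would more likely lower the response rate than raise it.
- That the 6-month look-ahead for radiation in 5.2.7 proves 5.1.4 inconsistent. It addresses a different hazard.

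**Conclusion.** The timing mismatch is certain from the text: the permitted swab can fall about 3 weeks beyond the AI horizon with same-day instruction, and later otherwise. No rule on eligibility, response, withdrawal or analysis closes that gap. The direction of any bias, toward a positive result, rests on the protocol's own rationale. Its size is unknown. On the stated assumptions, one affected woman moves the 3.3% error rate to 3.8–5.6%, crossing the 5% limit only if her chance of a spurious response is about 40% or more. Two move it to 4.4–9.0%. The design and sample size are sound as stated. This is a modest weakness, worth correcting because the remedy is cheap and the trial has no control arm to absorb it. The lubricant and window mismatch is a minor consistency point that would more likely dilute response than inflate it.

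**What to change.** 1. Reconcile 5.1.4 with the visit window. Either word the intention so that it covers the last permitted completion swab, 16 weeks after instruction, or narrow the late side of the window so that the 3 months cover it. Whichever is chosen, state the start point. This selects on plans that women already have and does not direct AI care.

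2. Add a sensitivity analysis to Section 11.3. Use the AI log to identify swabs taken after AI ended, report how many there were, and give the response rate again with those women counted as non-responders. This also covers unplanned stopping, which entry wording cannot prevent. Section 1.0 itself reports occasional to frequent non-adherence in 20–55% of women.

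3. Reconcile 7.2 with 4.5 and 9.4, and state whether the program continues until the visit when that falls after week 12. That choice belongs to the sponsor.

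The cost is a few lines of text and one extra tabulation of data already collected, with no change in sample size. Rewording 5.1.4 may lose the few women whose AI course ends between months 3 and 4. Narrowing the window instead gives up some scheduling flexibility. Counting off-AI women as non-responders is deliberately conservative and could understate a genuine response, so it belongs beside the primary result and should not replace it.

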5.2 Exclusion Criteria

Any potential subject who meets any of the following criteria will be excluded from participating in the study:

_____ **5.2.1** Pre-existing hypertonic pelvic floor dysfunction identified in the medical record

_____ **5.2.2** Unresolved or recurrent vaginismus identified in the medical record

_____ **5.2.3** Aversion to touching one's own body, including genitals, or using vibration therapy on the genitals

_____ **5.2.4** Currently receiving estrogen therapy, including topical and/or systemic estrogens

_____ **5.2.5** Have received estrogen therapy within 6 months of study enrollment, including topical and/or systemic estrogens

_____ **5.2.6** Any surgical procedure to the vagina or vulva, excluding office biopsies, within the previous 12 months

_____ **5.2.7** Receipt of pelvic or vaginal or vulvar radiation therapy within the 12 months prior to enrollment or if the subject is anticipated to receive radiation targeted to any of these 3

locations within 6 months following enrollment

5.2.8 Any use of the VRP off study within the last 6 months

6.0 DOSAGE AND ADMINISTRATION OF INTERVENTION

The VRP is a standardized program. The description has been put into pamphlet form and will be given to the subjects as part of the study materials.

For the external component, the program begins by instructing the subject to use a quarter-sized amount of moisturizing lubricant on the fingers. Using this moisturizer, a press-release motion is taught to be used over the entire vulva. This is repeated for the vaginal introitus. These activities are encouraged to be performed 3 to 4 days per week.

For the internal component, the instructor will select the appropriate size of the FDA-approved vibrating vaginal wand to be used in this study. The subject will be instructed in the proper lubrication of the vibrating wand and how to insert it to the deepest comfortable depth. When the vibration function is activated, the subject is instructed to find a comfortable position and allow a 5-minute vibration cycle. These activities are encouraged to be performed 3 to 4 days per week.

